PTSD Symptoms. Regardless of the causal relation between smoking and PTSD (i.e., PTSD leads to smoking³¹ or vice versa³²), there is evidence that smoking may help regulate PTSD symptoms and associated mood states. PTSD is an anxiety disorder involving an extreme and often sustained psychological and biochemical stress response to trauma exposure. Pervasive efforts to avoid distress are central to PTSD symptomatology. Regular self-administration of nicotine may serve as one strategy for tolerating PTSD-related symptoms (re-experiencing, avoidance, emotional numbing, hyperarousal). VA PTSD patients, in particular, report being motivated to smoke in response to distressing military memories¹⁴. They have also been shown to experience nicotine withdrawal symptoms in response to encounters with trauma-related stressors³³, and they report that smoking reduces PTSD symptoms elicited by exposure to laboratory-based trauma cues³⁴. In addition, research³⁵ including ours³⁶, shows that higher emotional numbing symptoms of PTSD (loss of interest, detachment from others) are associated with heavier smoking. These results suggest that smoking may be used to counteract the automatic blunting of positive emotion following trauma exposure.

Negative Affect. In addition to relatively specific PTSD symptoms, individuals with PTSD

also experience severe negative affective disturbances, and may smoke to regulate these events³⁷. In fact, compared with other smokers, those with PTSD have extraordinarily high levels of negative affect^{37,38}, react more strongly to stressors^{39,40}, and have a greater perceived need to blunt or suppress negative affect³⁸. Also, data show that smoking reduces negative affect among veterans with PTSD after they have been exposed to laboratory-based trauma cues⁴¹. If smoking helps regulate negative mood, quitting smoking may unmask heightened negative affect among smokers with PTSD. Negative affect is associated with failure to quit smoking (e.g., ⁵), and those with PTSD may experience withdrawal-related negative affect as particularly intolerable⁴², prompting a return to smoking.

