Positive Affect. Smokers with PTSD may also self-administer nicotine to counter deficient positive affect, a deficit that is central to the emotional numbing component of PTSD. Evidence shows that individuals with PTSD report lower global positive affect than do those without PTSD³⁷, potentially because their pervasive pattern of avoidance disrupts contact with positively reinforcing activities that engender positive emotions. Nicotine administration stimulates brain reward systems⁴³ and produces positive mood improvement among smokers⁴⁴. Thus, those with PTSD may rely on cigarettes as an accessible and reliable source of positive reinforcement. When veterans with PTSD attempt to quit smoking, they may be particularly likely to relapse because they miss the positive mood enhancing effects of cigarettes. Indeed, post-quit declines in positive affect have been implicated with difficulties quitting smoking^{45,46}. We posit that veterans with PTSD may increase their likelihood of quitting smoking by learning to engage in new, non-smoking, sources of positive reinforcement that enhance positive emotions. BA was chosen as a smoking cessation adjuvant because it increases engagement in valued life activities in order to increase contact with positive reinforcement.

In summary, smoking may regulate PTSD symptoms as well as two affective vulnerabilities associated with PTSD: elevated negative affect and low positive affect. Quitting smoking may interfere with such regulation and further exacerbate these vulnerabilities, prompting a return to smoking. Thus, an optimal smoking cessation treatment for PTSD may be one that augments standard smoking cessation treatment with strategies that address PTSD symptoms as well as withdrawal-related affective distress. We propose to examine whether behavioral activation (BA), a treatment that targets these PTSD-associated vulnerabilities, improves the efficacy of standard smoking cessation treatment among veterans with PTSD.

Behavioral activation was first developed as a treatment for depression

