One hundred and twenty participants will be enrolled. For inclusion in the study, participants must: 1) report smoking an average of 6 or more cigarettes daily for at least six months; 2) report a desire to quit smoking; 3) meet criteria for *current* PTSD; 4) speak and read English; 5) agree to participate in the study; and 6) be \geq 18 years old.

Participants will be excluded from the study based on the following: 1) meeting criteria for psychotic or bipolar disorder; 2) psychoactive substance abuse or dependence (excluding nicotine dependence) within the past 6 months; 3) inability to give informed, voluntary, written consent to participate; 4) current use of any pharmacotherapy for smoking cessation not

provided by the researchers during the quit attempt; 5) use of non-cigarette tobacco or nicotine products as a primary form of tobacco/nicotine use; 6) being currently suicidal or homicidal, as assessed by VA suicide/homicide template questions administered to all veterans; 7) being medically unable to use the nicotine patch or nicotine gum/lozenge; 8) psychotropic medication changes within 2 months of study initiation and during active treatment; 9) current engagement in evidence-based therapies for PTSD or depression; 10) pregnant or trying to become pregnant; or 11) incarceration.

In addition, we will inform participants that, for research purposes, we prefer that they remain on the same psychotropic medication regimen throughout the trial. However, if it is necessary for a participant to alter treatment for his/her welfare, we will ask the participant to notify us immediately. Such participants will remain in the trial, but primary study analyses will be conducted with such participants excluded.

Any concerns regarding nicotine patch, gum, or lozenge use will be reviewed by the study clinician, who may interview patients should further information be required. All women of childbearing potential will be required to agree to use an approved method of birth control to prevent pregnancy during the period of nicotine replacement therapy (NRT) use. Participants with suicidal or homicidal ideation at screening will be referred for VA psychiatric care, and they will be excluded from the study. Study candidates who express imminent intent for harm to self or others at any point in the study will be referred for VA emergency care.

Assessments

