The following assessments will be conducted during the study: 1) Screening/diagnostic assessments used to determine inclusion into the study, 2) baseline descriptive assessments, 3) smoking status assessments, 4) treatment effect assessments, and 5) treatment adherence assessments. See Table 1 for the schedule of assessments.

Table 1. Therapy and Assessment Schedule for the Study

	Baseline	Therapy Sessions									Follow-ups		
	V1	V2 Wk -4	V3 Wk -3	V4 Wk -2	V5 Wk -1	V6 Target Quit Day	V7 Wk 1 Post- quit	V8 Wk 2 Post- quit	V9 Wk 3 Post- quit	V10 Wk 4 Post- quit	PA1, 2 Wk 12,20 Post-quit	V11 Wk 26 Post- quit	
In-person Counseling (ST+BA or ST+HSE)		TS1	TS2	TS3	TS4	TS5	TS6	TS7	TS8				
Screening/Diagnostic Assessments													
PTSD phone screen (PC-PTSD)	X*												
Axis I Disorders (SCID-I)	X												
PTSD (CAPS)	X									X			
Depression (SCID-I)	X									X			
Suicidal/Homicidal Ideation Assessment	X												
Medical History	X												
Baseline Descriptive Measures													
Demographics	X												
Smoking history	X												
FTND	X												
WSWS	X												
Smoking Status Assessments													
Smoking/Alcohol use Status		X	X	X	X	X	X	X	X		X	X	
Calendar data		X	X	X	X	X	X	X	X		X	X	
CO assessment	X					X	X	X	X			X	
Cotinine Assessment												X	
Treatment Effects Assessments													
PANAS	X	X		X		X	X	X	X	X	X	X	
PTSD symptoms (PCL)	X			X		X	X	X		X	X	X	
Depressed mood (PHQ-9)	X								X				
Behavioral Activation (BAS)	X				X		X		X		X	X	
WSWS-11	X					X		X		X	X	X	

Tripartite Pleasure Scale	X				X		X			X		X
Snaith-Hamilton Pleasure	X			X		X		X		X	X	X
Stress and Pleasure	X								X		X	X
Treatment Adherence Measures												
Therapist adherence to treatment												
Adherence to nicotine patch and side effects						X	X	X	X		X (Wk 12 only)	
Participant adherence to BA		X	X	X	X	X	X	X	X			

*Occurs at the phone screen, prior to the in-person screening visit; **Follow-ups at Weeks 5 and 26 are in-person, to permit PTSD and depression assessments and abstinence bioverification, respectively. Other follow-ups, at Weeks 12 & 20, are phone assessments (PA).

Screening/Diagnostic Assessments

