Screening Telephone Call. Prior to entry into the study, participants will complete a screening phone call that will provide a brief overview of the study and ask preliminary screening questions. Study staff will obtain verbal consent to review the potential participant's VA medical chart to confirm that they meet basic criteria. The medical chart will be reviewed to confirm PTSD and depression diagnosis and treatment, other mental health disorders, current medications, and medication contraindications. Only information that is directly discussed with the potential participant will be recorded and no information regarding illicit drug use will be recorded. For those who are interested in learning more and who meet the criteria for entry into the study, an in-person screening session appointment (V1) will be scheduled.

In-Person Screening Assessment (V1). At the first visit, study staff will explain the study in detail and obtain written informed consent. Study staff will also obtain consent to audiotape treatment sessions on VA form 10-3203. For study candidates who provide informed consent, study staff will then proceed with screening and baseline assessments. All participants will complete an interview assessment including: 1) the Clinician Administered PTSD Scale (CAPS) for PTSD diagnostic status; 2) the Structured Clinical Interview for DSM (SCID) to assess for Axis I disorders (including depression); 3) assessment of suicidality or homicidality, and 4) medical history assessment. Any person who reports thoughts of suicide/self-harm or harm to others will be seen by VA Mental Health triage. Those judged to be at risk will be excluded and referred to appropriate VA treatment resources. Those who do not meet criteria for inclusion in the study will be referred to the VA smoking cessation clinic. Participants who meet inclusion/exclusion criteria will then be asked to complete a series of baseline self-report questionnaires including: 1) a demographic information questionnaire; 2) measures of PTSD symptom severity; 3) measures of proposed treatment effects; and 4) smoking history and dependence measures.

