The experimental treatment group will receive ST+BA, and the contact control group will receive ST+HSE. BA is being examined as an adjunct to ST, with the latter an evidence-based treatment for smoking cessation. Both treatments will be delivered in eight, individual therapy sessions. Treatment sessions 1–4 (V2–V5) will occur prior to the quit day, therapy session 5 (V6) will occur on the quit day, and therapy sessions 6–8 (V7–V9) will occur each week until 4 weeks post-quit (see Figure 4). Participants in the ST+BA and ST+HSE conditions will participate in 20 minutes of identical, standard smoking cessation treatment during each session. The ST+BA condition will include an additional 30 minutes of behavioral activation therapy, and the ST+HSE condition will include an additional 30 minutes of health and smoking education. In addition to receiving ST+BA or ST+HSE, all participants will receive 12 weeks of the nicotine patch and either nicotine gum or lozenge.

Standard Smoking Cessation Therapy (ST)

Participants in both treatment groups will receive a standard, individual smoking cessation treatment based on the 2008 US PHS Clinical Practice Guideline, *Treating Tobacco Use and Dependence*⁸⁶. The investigative team has considerable expertise in delivering behavioral and pharmacological treatments for smoking cessation. Treatment will be delivered in eight, 20-minute individual sessions over an 8-week period, with existing treatment manuals modified for this delivery format (see Table 2). The use of manuals will help ensure that the ST intervention does not differ between treatment arms (which will be checked with treatment fidelity assays). The same smoking cessation treatment has been used successfully in previous CTRI research (e.g., ^{4,46}). This cessation treatment is similar in content to that used at VA facilities¹⁸, increasing the generalizability of the current research.

Table 2. Standard Smoking Cessation Treatment Overview

Therapy Session	Standard Smoking Cessation Therapy Content
Therapy Session 1 (V2)	
 • Provide reinforcement and support for quitting. • Discuss past quit experiences. • Address pros and cons of quitting. • Initiate self-monitoring. • Provide self-help materials (Clearing the Air USDHHS) ¹⁰⁵
Therapy Sessions 2 (V3)	
 • Identify high-risk situations. • Discuss abstinence violation effect. • Develop coping strategies.

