We will also enhance retention via providing incentives for all phone assessment and in-person visits. Subjects will receive \$30 for each in-person treatment visit (V2–V9) to help defray the costs of travel or potential child care, \$25 for completing each follow-up phone assessment (at Weeks 12 and 20 post-quit (PA1–PA2)), and \$50 for attending each in-person follow-up visit (at Weeks 5 and 26 post-quit (V10–V11)). Participants will also receive \$2 for each automated call answered and an extra \$24 if they answer 80% or more of the automated calls. Total subject payment is thus \$450/subject if all visits, phone calls, and follow-ups are completed.

Data and Safety Monitoring Plan

To identify unanticipated problems or complications, study participants will be provided at enrollment with contact information for the study coordinator, principal investigator, and the VA hospital patient relations representative. Any unanticipated problems or complications will be reported to the MR IRB per UW-Madison campus policy. Corrective actions, such as changes to the research protocol or informed consent process, will be taken in order to protect the safety, welfare or rights of study subjects or others. Researchers will monitor biweekly for patient reports of affective distress and PTSD symptoms to inform decisions to stop treatment

early in consultation with the data monitoring committee. Additionally, the Clinical Science Research and Development (CSR) Data Monitoring Committee will review safety data.

Safety and Protection of Human Subjects

Subject privacy will be protected during the course of this study and HIPAA regulation will be followed. Only relevant, applicable study data will be collected, and will be entered in a secure web-based system with restricted access. Any required paper data will be kept in a confidential locked area, with no personal identifying information in our data set. This will be available only to primary study staff directly responsible for this data, and to representatives of the VA Research and Development Committee or University of Wisconsin IRB. Access to data will be removed if study staff are no longer part of the study team. Informed consent will be obtained by study staff. A data and safety monitoring committee will review all adverse events. Medical emergency and safety plans will be established, and adverse events will be reported in a timely manner to appropriate committees.

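### Suicidal and homicidal ideation is scheduled for assessment only at baseline, while the plan's rule for responding to harmful intent covers the whole study

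*Combined protocol and SAP*

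**What the plan says.** Table 1 lists "Suicidal/Homicidal Ideation Assessment" among the screening and diagnostic assessments, with one mark, at V1. The text agrees. The In-Person Screening Assessment (V1) includes "3) assessment of suicidality or homicidality, and 4) medical history assessment", and the Screening/Diagnostic Assessments section describes the instrument as a screening form whose results lead to exclusion, safety evaluation and referral.

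The Inclusion and Exclusion Criteria contain two rules. One applies at entry: "Participants with suicidal or homicidal ideation at screening will be referred for VA psychiatric care". The other has no time limit and sends for emergency care those who "express imminent intent for harm to self or others at any point in the study"; its grammatical subject is study candidates.

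On what may follow quitting, the Background says that "quitting smoking may unmask heightened negative affect among smokers with PTSD", and its summary adds: "Quitting smoking may interfere with such regulation and further exacerbate these vulnerabilities". In both places the stated consequence is a return to smoking.

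The Data and Safety Monitoring Plan provides for continuing oversight: "Researchers will monitor biweekly for patient reports of affective distress and PTSD symptoms to inform decisions to stop treatment". The section on reasons for stopping assigned treatment says much the same.

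**The concern.** The only scheduled question about ideation comes before therapy starts and before the participant quits. A rule that applies throughout the study depends on someone learning of intent, and the schedule names no point after V1 at which anyone asks.

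The population makes this worth attention. All participants have current PTSD, and major depression is a stratification factor, so depressed participants are expected. People currently engaged in evidence-based therapy for PTSD or depression are excluded, and the second recruitment pipeline seeks veterans who may not be receiving VA care. The trial therefore cannot assume that another clinician is asking.

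At stake is the detection of ideation that arises during the study, and what the safety committees can conclude. If ideation is not asked about, a report showing few or no cases is hard to read.

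**Working it through.** The plan gives no figure for this point, and no power or error-rate calculation bears on it. The check is a count from Table 1 and a comparison of provisions.

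**1. Scheduled contacts.** V1 to V11 are 11 visits; the calls at weeks 12 and 20 make 11 + 2 = 13. After V1 there are 13 − 1 = 12. From quit day (V6) onward there are V6 to V10 (5), two calls (2) and V11 (1): 5 + 2 + 1 = 8.

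**2. Contacts carrying the ideation form.** 1 of 13 overall, 0 of 12 after V1, 0 of 8 from quit day onward.

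**3. Timing.** Under Treatment Conditions Overview, "Treatment sessions 1–4 (V2–V5) will occur prior to the quit day", and V6 is quit day. V1 comes before V2 (week −4), so the span after V1 is at least 4 + 26 = 30 weeks, 26 of them after quitting. The form's homicidality example asks about the previous month, so at V1 it reaches no post-quit week.

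**4. Gaps late in the study.** V10 is at week 4 in the Table 1 header and week 5 in its footnote and in the retention section. The gaps are 12 − 5 = 7 or 12 − 4 = 8 weeks, then 20 − 12 = 8, then 26 − 20 = 6. After V10, Table 1 shows no contacts at a biweekly interval.

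**5. Could another provision do the same job?**

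| Provision | When | Described as asking about ideation? |
|---|---|---|
| Monitoring of reported distress and PTSD symptoms | Biweekly | No |
| Automated evening calls (Ecological Momentary Assessment) | 14 around quit day, 2 before therapy, 2 after it | No; six topics listed, ideation not among them |
| PANAS | 8 of the 8 contacts from quit day (Table 1) | No |
| PCL | 7 of the 8 (all but V9, by column position) | No |
| CAPS and SCID-I depression module | V10; referral if depression is noted and the participant is not already in care | No |
| PHQ | V9 only after baseline (Table 1) | No |
| Suicide-prevention training and psychologist on pager | Throughout | No; these support a response once risk is known |

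**6. Two inconsistencies in the same material.**
- *PHQ schedule.* Table 1 marks V1 and V9. The Background paragraph on the negative-affect treatment effect puts depressed mood at every study and follow-up visit. The Depressed Mood paragraph puts the PHQ in active treatment and follow-up, and the Follow-up section lists depressed mood among its measures.
- *Exclusion threshold.* The Inclusion and Exclusion Criteria exclude for ideation at screening. The description of the form excludes for homicidal ideation, or for suicidal ideation with intent or plan. The V1 description excludes those judged to be at risk. On the second wording, a person with suicidal ideation but no intent or plan could enroll, with no scheduled repeat of the form.

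**The case against.** The strongest reply is that the passages do not contradict each other. A form given once to settle eligibility, plus a rule for responding if intent is expressed later, is a coherent design, and the rule promises no repeated inquiry. That is correct: this is a gap in the schedule, not a contradiction.

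The second reply is that participants are closely followed. They have eight individual sessions, affect is measured at every contact from quit day, a clinical interview takes place at V10, adverse events are reviewed, and medical emergency and safety plans are to be established. This also stands, and it lowers the risk. But affect and symptom scores are not described as ideation questions, and the content of the safety plans is not given.

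Three stronger readings are tempting, and the documents do not support them.
- *That the plan itself names post-quit distress as a safety hazard.* The Background presents it as a cause of relapse and does not mention self-harm. The biweekly monitoring does treat distress as a reason to consider stopping treatment, but it does not mention ideation.
- *That the study-long rule can work only if a participant volunteers intent.* Therapists, interviewers and trained staff may well ask. The item content of the PHQ and the SCID-I module is not reproduced, so it cannot be said that no later contact touches on ideation, only that none is described as doing so.
- *That disclosure would differ by arm and spoil a comparison.* No between-arm analysis of ideation is planned. The session outlines do not settle the matter either: the BA sessions center on activities, values and goals, while the HSE sessions also cover psychological symptoms and relate content to the patient's life.

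**Conclusion.** The point holds as a gap in safety assessment: there is one scheduled ideation assessment, at V1, and none at the 8 contacts from quit day onward, against a response rule with no time limit. It should be corrected, but the existing safeguards make it a moderate matter.

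The conclusion rests on reading Table 1 by column position, which the V1 text supports for the ideation form, and on taking each instrument only as the documents describe it. If the PHQ or the SCID-I module does contain an ideation item with a defined response, the gap narrows at the visits where it is used; the plan would then need to say so. The documents give no expected rate of ideation, so the number of participants affected cannot be estimated.

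**What to change.** - In Table 1, add the existing suicidal/homicidal ideation form to contacts already scheduled from quit day onward. Its recall period needs checking, because a one-month look-back would not span gaps of 6 to 8 weeks.
- Name ideation in the biweekly monitoring, both in the Data and Safety Monitoring Plan and in the section on reasons for stopping assigned treatment, and in the safety reports to the committees.
- State how the monitoring is carried out after V10, given the contact schedule.
- Reconcile the PHQ schedule across Table 1, the Background, the Depressed Mood paragraph and the Follow-up section.
- Reconcile the three exclusion thresholds, and make clear that the study-long rule covers enrolled participants if that is meant.

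These changes concern assessment and reporting only. The thresholds and the action on a positive answer are for the sponsor to decide, and none is proposed here.

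The cost is an edit to Table 1 and a few sentences of text, plus an estimated few minutes per contact and some extra triage. The form, the staff training and the pager cover already exist.
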